### 7.1. Discontinuation from Study Treatment

#### 7.1.1. Discontinuation from Study Treatment

The following criteria must be followed for discontinuation from study treatment. Patients will enter into the Post-Treatment Follow-Up Period (Period 4) if they discontinue from study treatment.

- [1] Discontinuation of the investigational product for abnormal liver tests should be considered by the investigator when a patient meets one of the following conditions, after consultation with the Lilly designated medical monitor:
  - ALT or AST >8xULN
  - ALT or AST >5xULN for more than 2 weeks
  - ALT or AST >3xULN and total bilirubin level >2xULN or prothrombin time >1.5xULN
  - ALT or AST >3xULN with the appearance of fatigue, nausea, vomiting, right upper-quadrant pain or tenderness, fever, rash, and/or eosinophilia (>5%)
  - alkaline phosphatase >2.5xULN and total bilirubin >2xULN
  - alkaline phosphatase >2.5xULN with the appearance of fatigue, nausea, vomiting, right upper quadrant pain or tenderness, fever, rash, and/or eosinophilia (>5%)
- [2] Other laboratory tests (**Note:** Laboratory test(s) that may result in discontinuation based on a single result may be repeated only once if there is a technical error or clinical reason to believe a result may need to be retested. Laboratory tests can only be repeated after consultation with Lilly medical. Investigational product should not be administered in these cases until retest result is available.):
  - Neutrophil (segmented) counts (see safety monitoring for neutropenia in Section [8.4.10.1](#)):

- $<500$  cells/ $\mu\text{L}$  ( $<0.50 \times 10^3/\mu\text{L}$  or  $<0.50$  GI/L)
  - $\geq 500$  and  $<1000$  cells/ $\mu\text{L}$  ( $\geq 0.50 \times 10^3/\mu\text{L}$  and  $<1.00 \times 10^3/\mu\text{L}$  or  $\geq 0.50$  GI/L and  $<1.00$  GI/L) (based on 2 test results; the second test performed within 1 week from knowledge of the initial result)
  - $\geq 1000$  and  $<1500$  cells/ $\mu\text{L}$  ( $\geq 1.00 \times 10^3/\mu\text{L}$  and  $<1.50 \times 10^3/\mu\text{L}$  or  $\geq 1.00$  GI/L and  $<1.50$  GI/L) (based on 3 test results as specified in Section 8.4.10.1)
    - AND - a concurrent infection
  - Total WBC count  $<2000$  cells/ $\mu\text{L}$  ( $<2.00 \times 10^3/\mu\text{L}$  or  $<2.00$  GI/L)
  - Lymphocyte count  $<500$  cells/ $\mu\text{L}$  ( $<0.50 \times 10^3/\mu\text{L}$  or  $<0.50$  GI/L)

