#### **8.4.10. Safety Monitoring**

Lilly will periodically review evolving aggregate safety data within the study by appropriate methods.

If a study patient experiences elevated ALT  $\geq 3 \times \text{ULN}$ , alkaline phosphatase  $\geq 2 \times \text{ULN}$ , or elevated total bilirubin  $\geq 2 \times \text{ULN}$ , clinical and laboratory monitoring is to be initiated by the investigator. Details for hepatic monitoring depend upon the severity and persistence of observed laboratory test abnormalities. For other AESIs or abnormal lab results, please refer to the appropriate protocol section that addresses these topics. To ensure patient safety and comply with regulatory guidance, the investigator is to consult with the Lilly clinical research physician/clinical research scientist regarding collection of specific recommended clinical information and follow-up laboratory tests (see [Appendix 4](#)).

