	
baseline value is $\leq 1 \times \text{ULN}$, $> 1 \times \text{ULN}$ to $< 1.5 \times \text{ULN}$, $\geq 1.5 \times \text{ULN}$, or missing.
 
 ○ The analysis of $2 \times \text{ULN}$ will contain 5 subsets: patients whose nonmissing maximum baseline value is $\leq 1 \times \text{ULN}$, $> 1 \times \text{ULN}$ to $< 1.5 \times \text{ULN}$, $\geq 1.5 \times \text{ULN}$ to $< 2 \times \text{ULN}$, $\geq 2 \times \text{ULN}$, or missing. ● ALP: maximum postbaseline measurement > 1.5 times ($1.5 \times$) the Performing Lab ULN for all patients with a postbaseline value, and divided into 4 subsets: patients whose nonmissing maximum baseline value is $\leq 1 \times \text{ULN}$, $> 1 \times \text{ULN}$ to $\leq 1.5 \times \text{ULN}$, $> 1.5 \times \text{ULN}$, or missing. 	
	
Shift for ALT, AST, and total bilirubin from maximum baseline to maximum postbaseline will be produced with the requirements using Performing Lab Reference Ranges:
 
 ● Include scheduled visits, unscheduled visits, and repeat measurements. ● Use the maximum nonmissing value in the baseline period. ● Use the maximum nonmissing postbaseline value within each study period. ● Categories are: 
 ○ ALT: $\leq 1 \times \text{ULN}$, > 1 to $< 3 \times \text{ULN}$, ≥ 3 to $< 5 \times \text{ULN}$, ≥ 5 to $< 10 \times \text{ULN}$, ≥ 10 to $< 20 \times \text{ULN}$, and $\geq 20 \times \text{ULN}$ ○ AST: $\leq 1 \times \text{ULN}$, > 1 to $< 3 \times \text{ULN}$, ≥ 3 to $< 5 \times \text{ULN}$, ≥ 5 to $< 10 \times \text{ULN}$, ≥ 10 to $< 20 \times \text{ULN}$ and $\geq 20 \times \text{ULN}$ ○ Total bilirubin: $\leq 1 \times \text{ULN}$, > 1 to $< 1.5 \times \text{ULN}$, ≥ 1.5 to $< 2 \times \text{ULN}$, $\geq 2 \times \text{ULN}$ ○ ALP; $\leq 1 \times \text{ULN}$, > 1 to $\leq 1.5 \times \text{ULN}$, $> 1.5 \times \text{ULN}$ ● With additional categories: 
 ○ Decreased: postbaseline category $<$ baseline category ○ Increased: postbaseline category $>$ baseline category ○ Same: postbaseline category = baseline category 	
Period 2, Period 3 (Summary) and Combined Periods 2 and 3 (Summary): Shifts from maximum baseline to maximum postbaseline category

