	
Elevated hepatic criteria: maximum ALT $\geq 3 \times \text{ULN}$ and maximum total bilirubin $\geq 2 \times \text{ULN}$ using Performing Lab Reference Ranges.
 
Listing of patients who meet any of the following criteria:
 
 ● Elevated hepatic criteria: defined as maximum ALT $\geq 3 \times \text{ULN}$ and maximum total bilirubin $\geq 2 \times \text{ULN}$, ● An ALT or AST $\geq 3 \times \text{ULN}$ ● An ALP $\geq 1.5 \times \text{ULN}$ ● A total bilirubin $\geq 2 \times \text{ULN}$ 
The listing will include: patient demographics, concomitant medications, ALT/AST/ALP/total bilirubin/GGT by visit, treatment start and stop dates, and reason for treatment discontinuation.
	
Period 2 (Fisher’s exact test), Period 3, and Period 4 (Summary): Elevated hepatic criteria Listing: Elevations in hepatic laboratory tests (to be prepared in Spotfire)

Special Safety Topic	Definition / Derivation	Analysis / Summary / Listing
	Evaluation of Drug-Induced Serious Hepatotoxicity (eDISH) plot: use maximum ALT measurement and maximum total bilirubin measurement with patients having at least 1 postbaseline ALT and total bilirubin, which contributes 1 point to the plot. The measurements do not need to be taken at the same blood draw.	Period 2: eDISH plot (to be prepared in Spotfire)
Cytopenias	Cytopenias are defined using the PTs from the following 2 sub-SMQs of the Haematopoietic cytopenias SMQ (20000027) as specified in MedDRA: 
 • Broad and narrow terms in the Haematopoietic leukopenia (20000030) • Broad and narrow terms in the Haematopoietic thrombocytopenia (20000031) 	Period 2 (Fisher's exact test), Period 3 (Summary) and Combined Periods 2 and 3 (Summary): TEAE by PT within sub-SMQ, Listing (to be prepared in Spotfire): TEAE (included in the same listing with hepatic, depression and interstitial lung disease AESIs)
Infections	Infections are events including all infections (defined using all the MedDRA PTs from the Infections and infestations OSC), serious infections, potential opportunistic infections, and infections resulting in anti-infective medication administration (ie, antibacterial, antivirals, antifungals, antiparasitic treatments).	Period 2 (Fisher's exact test), Period 3 (Summary) and Combined Periods 2 and 3 (Summary): SAE by PT, AE leading to treatment discontinuation by PT (Period 2 only)

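### The SAP's combined liver-test count and the eDISH axis use ALT alone, so a patient with raised AST and bilirubin but ALT below 3xULN is not counted

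*SAP*

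**What the plan says.** **SAP, combined criterion.** In the hepatic part of Table RHBW.6.8 (SAP 6.12.3.1), the combined criterion starts "Elevated hepatic criteria: maximum ALT" and needs a maximum ALT of at least 3xULN together with a maximum total bilirubin of at least 2xULN. It is tested with Fisher's exact test in Period 2 and summarised afterwards: "Period 3, and Period 4 (Summary): Elevated hepatic criteria".

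**SAP, eDISH.** The Period 2 plot is to "use maximum ALT measurement and maximum total bilirubin measurement", one point per patient who has a postbaseline value of each. The two values need not come from the same blood draw.

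**SAP, other hepatic laboratory outputs.** The elevation table applies the same cut-offs (3, 5, 10 and 20xULN) to ALT and AST and covers Periods 2 and 3. The shift tables include both enzymes for Periods 2, 3 and the two combined. The listing is triggered by ALT or AST at 3xULN, by ALP at 1.5xULN, or by bilirubin at 2xULN, and shows all of these by visit. For ALP the elevation rule ("ALP: maximum postbaseline measurement") has one cut-off, 1.5xULN, and no table pairs ALP with bilirubin.

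**Protocol 7.1.1, item [1].** Two of its conditions are "ALT or AST >3xULN and total bilirubin level >2xULN or prothrombin time >1.5xULN" and "alkaline phosphatase >2.5xULN and total bilirubin >2xULN". Protocol 8.2.2 names ALT, AST, bilirubin and alkaline phosphatase together in the hepatic adverse event of special interest.

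**The concern.** Within the hepatic outputs, the combined count and the eDISH plot are where AST drops out, and the SAP gives no reason. They are also the only two outputs that look at an aminotransferase and bilirubin jointly. The separate AST and bilirubin tables are marginal counts: one patient in each does not tell the reader whether it is the same patient.

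The expected count in such a table is zero or close to it. One uncounted patient can therefore turn a row that should read one into a row that reads none, for a named event of special interest. Period 4 is the most exposed. SAP 6.12.3.1 makes hepatic laboratory tests the exception to its general rule of no special-interest summaries in follow-up, and the only hepatic laboratory summary it then specifies for that period is the ALT-based one.

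**Working it through.** No sample size, power or error rate is involved, and the plan states no figure to reproduce. The check applies each rule to hypothetical patients. All values are multiples of ULN and are assumed for illustration; prothrombin time is normal (1.0) unless shown.

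Rules applied:
- Protocol 7.1.1, aminotransferase limb: (ALT > 3 or AST > 3) and (bilirubin > 2 or prothrombin time > 1.5)
- SAP combined criterion: ALT ≥ 3 and bilirubin ≥ 2
- SAP single-analyte tables: AST ≥ 3; bilirubin ≥ 2
- SAP listing: ALT ≥ 3 or AST ≥ 3 or bilirubin ≥ 2 (the ALP trigger is not needed here)
- eDISH: every patient is plotted at (ALT, bilirubin). The SAP gives no reference lines, so the combined-elevation region is taken as ALT ≥ 3 and bilirubin ≥ 2.

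| Patient | Protocol 7.1.1 | SAP combined count | AST ≥ 3 table | Bilirubin ≥ 2 table | Listing | eDISH |
|---|---|---|---|---|---|---|
| ALT 2, AST 4, bilirubin 2.5 | yes | **no** | yes | yes | yes | plotted at (2, 2.5), outside region |
| ALT 4, AST 2, bilirubin 2.5 | yes | yes | no | yes | yes | plotted at (4, 2.5), inside |
| ALT 4, AST 4, bilirubin 2.5 | yes | yes | yes | yes | yes | plotted at (4, 2.5), inside |
| ALT 3, AST 1, bilirubin 2 | no | yes | no | yes | yes | plotted at (3, 2), on the boundary |
| ALT 2, AST 4, bilirubin 1, prothrombin time 1.6 | yes | no | yes | no | yes | plotted at (2, 1), outside |

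The first two rows exchange the ALT and AST values and nothing else, yet only the second patient is counted. The fourth row shows that the SAP's ≥ is slightly wider than the protocol's > at the boundary, so the two rules differ in that respect as well. The fifth shows that the prothrombin alternative is outside the SAP count whichever enzyme is used.

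**Effect of adding AST.** With the criterion (ALT ≥ 3 or AST ≥ 3) and bilirubin ≥ 2, the first patient becomes counted because 4 ≥ 3 and 2.5 ≥ 2. The eDISH point stays at (2, 2.5) unless the axis changes too; with max(ALT, AST) it moves to (4, 2.5).

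**Period 4.**
1. Protocol Appendix 2 schedules serum chemistry at Visits 801, 802 and 803, and Appendix 3 lists ALT, AST, ALP and total bilirubin under serum chemistry. The data are collected.
2. Table RHBW.6.8 gives the elevation table for Periods 2 and 3 and the shift tables for Periods 2, 3 and combined 2 and 3. Neither covers Period 4.
3. SAP 6.12.4 removes ALT, AST, total bilirubin and ALP from the general treatment-emergent and follow-up-emergent abnormality summary, because 6.12.3.1 deals with them.
4. That leaves the ALT-based combined criterion as the specified Period 4 summary. The first patient, if the elevations arise in follow-up, is found only in the listing. This assumes that the listing, which states no period, includes Period 4.

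**The case against.** The case for leaving the plan alone has real content.

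- **Protocol 7.1.1 governs conduct, not analysis.** Its lead-in is "Discontinuation of the investigational product for abnormal liver tests should be considered by the investigator when a patient meets one of the following conditions". Protocol 9.5 and 9.5.2 define no combined hepatic endpoint and leave detail to the SAP. SAP Table RHBW.6.12 uses the 7.1.1 condition only for a deviation, item [D1]. This stands: nothing obliges the safety table to mirror 7.1.1.
- **ALT alone has some basis in the protocol.** The monitoring trigger in Protocol 8.4.10 begins "If a study patient experiences elevated ALT" and adds alkaline phosphatase and bilirubin, without AST. This stands. AST also has non-hepatic sources, which is a legitimate reason for preferring ALT; the SAP does not state it.
- **The patient is visible elsewhere.** For very few patients, a by-visit listing with AST, ALP and bilirubin side by side is informative. This stands for individual review. It does not supply a between-group count of the combination.
- **Clinical events are reported too.** Hepatic adverse events are summarised through five MedDRA queries in the treatment periods, and follow-up-emergent events by preferred term in Period 4. This stands for reported events, but a laboratory elevation with no reported event would not appear there.
- **The program safety analysis plan may supersede the table.** SAP 6.12.3.1 says so, and that document is not available here. It may already deal with AST.

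A reader might infer that an AST-driven case disappears from the hepatic outputs, or from the eDISH plot. The documents do not support that: the patient is plotted, with the bilirubin elevation showing, but positioned by ALT. Nor do they support reading the SAP as contradicting the protocol, since the two rules serve different purposes.

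**Conclusion.** A minor reporting gap, worth closing because it is cheap to close. The combined count in Periods 2, 3 and 4 and the eDISH axis in Period 2 ignore AST, although the SAP's elevation, shift and listing rules give AST equal standing. What is lost is the tabulated count of patients with both elevations when AST is the driver. In Periods 2 and 3 the marginal tables and the listing still show the pieces; in Period 4 only the listing does.

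The size cannot be computed, because neither document gives a rate of AST-predominant elevation with raised bilirubin. As an assumption only, 0 to 2 patients among about 300 randomised would be at most 2/300 = 0.7%. No efficacy conclusion, error rate or formal safety decision rests on this count. A reader might infer that a hepatic signal would be concealed; that goes beyond the documents, since the listing captures every such patient.

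**What to change.** In Table RHBW.6.8:

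1. Keep the existing ALT row. Beside it add a row for maximum ALT or AST ≥ 3xULN with maximum total bilirubin ≥ 2xULN, for Periods 2, 3 and 4, with Fisher's exact test in Period 2 as now.
2. In eDISH, add an AST panel, or plot the larger of ALT/ULN and AST/ULN against bilirubin.
3. Optionally, add a row pairing ALP with bilirubin at the thresholds already written in Protocol 7.1.1 (above 2.5xULN and above 2xULN).
4. Align the program safety analysis plan, since it can override this table. If ALT alone is kept, state the reason.

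The new row would not reproduce all of 7.1.1: the prothrombin and symptom limbs stay outside it, and its label should not suggest otherwise. The cost is a few lines of specification and programming on data already collected. The downside is a few extra flagged patients whose AST has a non-hepatic source; the retained ALT row lets the reader tell them apart. No discontinuation or monitoring rule changes.

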### **8.2.2. Adverse Events of Special Interest**

The following adverse events of special interest (AESIs) will be used to determine the safety and tolerability of ixekizumab over the range of doses selected for this clinical study.

The AESIs for ixekizumab are:

- cytopenias (leukopenia, neutropenia, and thrombocytopenia)
- clinically significant hepatic events and/or significant elevations in liver function test changes/enzyme elevations (ALT, AST, bilirubin, and alkaline phosphatase)
- infections
- injection site reactions
- allergic reactions/hypersensitivities
- cerebrocardiovascular events
- malignancies
- IBD
- depression.

Sites will provide details on some of these AEs as instructed on the CRF. Investigators will also educate patients and/or caregivers about the symptoms of allergic/hypersensitivity reactions and will provide instructions on dealing with these reactions (see also Section 6.6.1). A blood sample is to be collected as soon as possible for any patient who experiences an AE of a potential systemic allergic/hypersensitivity reaction during the study as judged by the investigator.

Data on preferred terms associated with cerebrocardiovascular events (defined as death, cardiac ischemic events including MI and hospitalization for unstable angina, hospitalization for heart failure, serious arrhythmia, resuscitated sudden death, cardiogenic shock, coronary revascularization procedure, stroke/transient ischemic attack, peripheral revascularization procedure, and peripheral arterial event and hospitalization for hypertension) will be collected, and these events and any deaths will be adjudicated by an external Clinical Events Committee (CEC) made up of a chairman, 2 cardiologists, and a neurologist.

Data on suspected IBD, as identified by events possibly indicative of ulcerative colitis and Crohn's disease, will be collected and the events will be adjudicated by an external CEC with expertise in IBD.

The role of external CECs is to adjudicate defined clinical events in a blinded, consistent, and unbiased manner throughout the course of a study. The purpose of the CEC for adjudication of cerebrocardiovascular events and the CEC for adjudication of suspected IBD events is to ensure that all reported events are evaluated uniformly by a single group.

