### **9.5. Safety Analyses**

Safety will be assessed by summarizing and analyzing AEs including adjudicated cerebrocardiovascular events, laboratory analytes including neutrophil counts, QIDS-SR16, C-SSRS, and vital signs. The duration of treatment exposure will also be summarized.

For Period 2 (Blinded Treatment Dosing Period), safety data will be summarized for the Safety Population. Treatment group comparisons will be performed on categorical safety data using Fisher's exact test as described in Section 9.2.1; continuous safety data will be analyzed by an ANCOVA model.

For Period 3 (Extended Treatment Period), the safety data will be summarized and no treatment group comparisons will be performed.

For Period 4 (Post-Treatment Follow-Up Period), safety data will be summarized according to the treatment patients were on prior to entering Period 4.

The categorical safety measures will be summarized with incidence rates. The mean change of the continuous safety measures will be summarized by visits.

Further details will be described in the SAP.

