Cerebro-cardiovascular Events	
Cerebro-cardiovascular events will be externally adjudicated by the Central Events Committee (CEC) at the Cleveland Clinic, as outlined in the Manual of Operations. The CEC will adjudicate investigator-reported events selected for adjudication and render an assessment as to whether the event represents a confirmed event (meeting the event definition with all necessary documentation), a nonevent (does not meet the event definition and likely represents an alternative or nonevent diagnosis), or lacks sufficient documentation for confirmation of an event. All events which qualify for CEC adjudication will be used for the analysis of cerebro-cardiovascular events. The categories and subcategories of adjudicated events used for the analysis will include the following:
 
 • Cardiovascular 
 ○ Death (cardiovascular) ○ Cardiac ischemic event: myocardial infarction and hospitalization for unstable angina ○ Serious arrhythmia ○ Hospitalization for heart failure ○ Hospitalization for hypertension ○ Resuscitated sudden death ○ Cardiogenic shock ○ Coronary revascularization • Neurologic 
 ○ Cerebrovascular Event: Transient Ischemic Attack or Stroke (Hemorrhagic, Ischemic and Undetermined) • Peripheral Vascular Events 	
Period 2 (Fisher’s exact test), Period 3 (Summary) and Combined Periods 2 and 3 (Summary): TEAE by PT within Subcategory, Listing (to be prepared in Spotfire): TEAE

Special Safety Topic	Definition / Derivation	Analysis / Summary / Listing
	
 ○ Peripheral arterial event ○ Peripheral revascularization 
Events will be analyzed using MedDRA PT nested within the CEC assessment (confirmed event, no event, or insufficient documentation for event determination) and the subcategory. Subtypes of stroke (Hemorrhagic Stroke , Ischemic Stroke, and Undetermined Stroke Type) will be displayed in the analyses nested within Cerebrovascular Event. Subtypes of Serious Arrhythmia (Atrial Arrhythmia, Ventricular Arrhythmia, Heart Block, Other, Unknown) will be displayed nested within Serious Arrhythmia.
	

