	
Events will be summarize by the following categories:
 
 • Nonmelanoma Skin Cancer (NMSC) 
 ○ Basal Cell Carcinoma, PTs include: 
 ▪ Basal cell carcinoma ▪ Basosquamous carcinoma ▪ Basosquamous carcinoma of skin ○ Squamous Cell Carcinoma, PTs include: 
 ▪ Squamous cell carcinoma of skin ▪ Bowen’s disease ▪ Lip squamous cell carcinoma ▪ Skin squamous cell carcinoma metastatic ▪ Keratoacanthoma • Malignancies excluding NMSC: all PTs in the Malignant or unspecified tumors SMQ excluding the 8 defined NMSC PTs. 	
Depressions	
Depression is defined using the PTs from the Depression and suicide/self-injury SMQ as specified in MedDRA (SMQ: 20000035, which includes the sub-SMQs: 20000037 [Suicide/self-injury] and 20000167 [Depression (excluding suicide and self-injury)]).
	
Period 2 (Fisher’s exact test) and Period 3 (Summary): TEAE by PT within SMQ and sub-SMQ, Listing (to be prepared in Spotfire): TEAE (included in the same listing with hepatic, cytopenia and interstitial lung disease AESIs)

Inflammatory Bowel Disease (IBD)	
IBD will be identified using the following subcategory and MedDRA PTs: The narrow terms are considered IBD.
 
IBD (Narrow terms)
 
 • Inflammatory Bowel Disease: Inflammatory bowel disease • Crohn’s Disease: Crohn’s disease • Ulcerative Colitis: Acute haemorrhagic ulcerative colitis; Colitis ulcerative; Proctitis ulcerative 
Non-Specific Terms Events That Can Occur with IBD (Broad Terms)): The PTs in this category are
	
Period 2 (Fisher’s exact test), Period 3 (Summary) and Combined Periods 2 and 3 (Summary): TEAE by PT within subcategory, Listing (to be prepared in Spotfire): TEAE

Special Safety Topic	Definition / Derivation	Analysis / Summary / Listing
	listed in Appendix 10 .	

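### Suspected IBD goes to an external expert committee, but no analysis in the protocol or SAP as supplied uses its verdicts: the SAP classifies IBD by preferred term alone

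*SAP*

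**What the plan says.** Protocol Section 8.2.2 lists IBD as an adverse event of special interest. For suspected IBD it says that "the events will be adjudicated by an external CEC with expertise in IBD". It gives the purpose as follows: the "CEC for adjudication of suspected IBD events is to ensure that all reported events are evaluated uniformly by a single group".

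The IBD row of SAP Table RHBW.6.8 (Section 6.12.3.1) sets the classification rule. It opens with "IBD will be identified using the following subcategory and MedDRA PTs" and continues "The narrow terms are considered IBD". The remaining terms form a broad group of non-specific events, listed in Appendix 10. The planned output is "TEAE by PT within subcategory", with Fisher's exact test in Period 2 and summaries for Period 3 and for Periods 2 and 3 combined, plus a listing of treatment-emergent events. The row does not mention the committee.

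The cerebro-cardiovascular row of the same table does: "All events which qualify for CEC adjudication will be used for the analysis of cerebro-cardiovascular events", and "Events will be analyzed using MedDRA PT nested within the CEC assessment".

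On adjudicated events, Protocol Section 9.5 says only that safety will be assessed by "summarizing and analyzing AEs including adjudicated cerebrocardiovascular events". It does not name adjudicated IBD.

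**The concern.** The protocol arranges blinded expert classification of suspected IBD, and the analysis plan then counts IBD from the coded term. If the rule is followed literally, the coded term and the committee verdict can disagree, and the tables would not show it.

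Expert classification matters in this population. Past or present Crohn's disease or ulcerative colitis is a qualifying spondyloarthritis feature (Protocol Appendix 5). Exclusion criterion 13 admits patients with a history of IBD who have had no exacerbation for at least 6 months. A bowel complaint in such a patient could be a true flare or something else.

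At stake is the reported IBD frequency for one adverse event of special interest. No efficacy conclusion depends on it.

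**Working it through.** The plan states no figure for IBD, so there is nothing to reproduce. The check is a comparison of texts, followed by a small illustration of scale.

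**1. How Table RHBW.6.8 treats topics that receive review**

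| Topic | Who reviews | How the result enters the analysis |
|---|---|---|
| Cerebro-cardiovascular events | External committee | Preferred term nested within verdict: confirmed, not an event, or insufficient documentation |
| Major adverse cerebro-cardiovascular events | External committee | Built from the adjudication eCRF pages |
| Opportunistic infections | Medical review | Narrow terms count unless review overturns them; broad terms need review before they count |
| IBD | External committee (Protocol 8.2.2) | None stated; the narrow term decides |

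The output column does not explain the difference, because both the cerebro-cardiovascular row and the IBD row ask for treatment-emergent events by preferred term within subcategory. The verdict layer for cerebro-cardiovascular events is in the definition column. The IBD definition has no equivalent.

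**2. Search for the verdicts elsewhere.** Protocol 9.5 mentions only cerebro-cardiovascular adjudication. SAP 6.12 names no adjudicated events. Appendix 10 is redacted, but its title describes a preferred-term list and the IBD row cites it only for the broad terms.

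**3. What the written rule does in the two discordant cases**

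- Narrow term, rejected by the committee: counted as IBD.
- Broad term, confirmed by the committee: tabulated among non-specific terms and not labelled as confirmed.

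Neither the narrow table nor the pooled narrow-plus-broad table gives the number of confirmed cases.

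**4. Timing.** The current protocol is dated June 2017 and SAP Version 4 February 2019. The SAP revision history records an update of the IBD wording at Version 2. The row was therefore revisited and still has no verdict layer.

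**5. Scale (illustration only).** About 300 patients at 1:1:1 gives 300/3 = 100 per arm. One case is 1/100 = 1 percentage point in each regimen-versus-placebo comparison. Pooled over the two ixekizumab arms it is 1/200 = 0.5 points.

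Two-sided Fisher's exact tests at 100 versus 100, with hypothetical counts:

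| Events | p |
|---|---|
| 5 vs 0 | 0.059 |
| 6 vs 0 | 0.029 |
| 7 vs 1 | 0.065 |
| 8 vs 1 | 0.035 |

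One reclassified event can move such a comparison across 0.05. The documents do not say whether counts of this order are likely.

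**The case against.** The strongest reply is that the controlling document may lie elsewhere. SAP 6.12.3.1 says that if the terms or the analysis for a special safety topic change, the change is recorded in the program safety analysis plan, which then takes precedence without an SAP amendment. That covers analyses as well as term lists, and the plan was not supplied. A reader might infer that the verdicts are never used at all. The documents do not support that; they show only that the protocol and SAP as supplied state no use.

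Second, the SAP follows the protocol's own analysis sections. Protocol 9.5.1 identifies events of special interest by standardised query or a sponsor-defined term list, and Section 8.2.2 promises adjudication without promising an analysis by verdict. This stands: the gap lies between the protocol's collection and analysis sections and carries into the SAP. It is not an SAP rule that contradicts the protocol's analysis plan.

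Third, broad-term events are not dropped. Section 6.12.3.1 calls for both a narrow and a pooled narrow-plus-broad summary, so a confirmed case coded to a listed broad term is still tabulated. This also stands, but the case carries no label as confirmed.

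Fourth, a history of IBD does not show that narrow terms misclassify. Active disease is excluded, and a pre-existing condition becomes treatment-emergent only if it worsens. That is fair: the history makes expert classification useful but proves no error.

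**Conclusion.** The point holds as a reporting gap and should be fixed. The protocol requires IBD verdicts, the SAP states a counting rule that ignores them, and neither document as supplied assigns them an analysis.

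The size cannot be computed, because the documents give neither an IBD rate nor a confirmation rate. The figure of 1 percentage point per case assumes about 100 patients per arm, and the Fisher examples use invented counts.

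Two stronger readings are tempting and go too far. A reader might infer that the IBD rate is misclassified in both directions. The rule permits each kind of error, but nothing shows that either occurs. A reader might also infer that the cerebro-cardiovascular row makes confirmed events the main summary. It does not: it displays all adjudicated events by verdict.

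The comparisons concerned carry no multiplicity adjustment, and no primary or major secondary conclusion changes. The conclusion would fall away if the program safety analysis plan already specifies an analysis by verdict. In that case a cross-reference in the IBD row would be enough.

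**What to change.** In the IBD row of SAP Table RHBW.6.8:

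- Add a summary of all adjudicated IBD events by preferred term nested within the committee's assessment (confirmed, not an event, insufficient documentation), in the same form as the cerebro-cardiovascular row.
- Add the committee verdict to the IBD listing.
- State which count, adjudicated or term-based, will support the IBD conclusion.
- Keep the narrow and broad preferred-term tables.

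If the program safety analysis plan already covers this, cite it in the row.

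The cost is SAP wording and one extra table. The protocol already requires the adjudication, so no new data collection is needed. The documents do not say whether adjudication has been completed.
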